2.1 Design overview

This efficacy trial adopts a two-arm, two-level design with pupils clustered into schools. The unit of randomisation is the school. All pupils in Year 8 in the participating schools undertake baseline tests from November 2023 to January 2024 and outcome tests at the follow-up stage in March 2025. The schools within the control group continue to function according to business-as-usual. There is no waitlist design in this trial.

The randomisation process adopts the minimisation approach considering whether the percentage of students eligible for free school meals (FSM6) at each school fell above or below the median percentage of FSM6 across all schools in the sample. More detail is discussed in the next section.

The randomisation process was executed by colleagues from the University of Kent, operating independently from the evaluation team at Ipsos UK. The University of Kent was provided with a list of schools without school names but marked with ID codes, ensuring they could not discern the schools' identities, thus maintaining blindness during the randomisation procedure. The randomisation procedure occurred in two phases: one in early December 2023 and another in January 2024. Initially, the intention was to conduct baseline testing for

all schools in November and proceed with randomisation in December. However, extending the timeline became imperative to accommodate additional time for recruitment, data collection, fieldwork, and the constraints posed by the Christmas break and Ofsted inspections, allowing schools ample opportunity to implement the surveys.

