- ERQ7: What is the mean difference in the sense of connectedness, measured by the School Connectedness Scale, between CYP in intervention settings receiving TISUK training and CYP in control settings receiving business as usual at follow-up?
- ERQ8: What is the mean difference in the percentage of exclusions between CYP in intervention settings receiving TISUK training and CYP in control settings receiving business as usual at follow-up?
- ERQ9: What is the mean difference in the percentage of suspensions between CYP in intervention settings receiving TISUK training and CYP in control settings receiving business as usual at follow-up?
- ERQ10: What is the mean difference in the percentage of attendance between CYP in intervention settings receiving TISUK training and CYP in control settings receiving business as usual at follow-up?

- ERQ11: What is the mean difference in all primary and secondary CYP outcomes between CYP in intervention settings who received TISUK training and CYP in control settings who received business as usual, considering sub-group analysis by sex, ethnicity, and free school meal (FSM) eligibility?

School staff level

- ERQ12: What is the difference in attitudes related to trauma-informed care (TIC) of school staff, measured by the Attitudes Related to Trauma-Informed Care (ARTIC) survey, between school staff in the intervention setting receiving TISUK training and school staff in control settings receiving business as usual at follow-up?
- ERQ13: What is the difference in well-being, measured by the SWEMWBS, between school staff in the intervention setting receiving TISUK training and school staff in control settings receiving business as usual at follow-up?

School level

- ERQ14: What is the difference in the percentage of school staff retention at the school level between schools in the intervention setting receiving TISUK training and schools in control settings receiving business as usual at follow-up?
- ERQ15: What is the difference in the percentage of school staff sickness at the school level between schools in the intervention setting receiving TISUK training and schools in control settings receiving business as usual at follow-up?
- ERQ16: What is the difference in the percentage of CYP suspensions at the school level between schools in the intervention setting receiving TISUK training and schools in control settings receiving business as usual at follow-up?

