Secondary outcomes will be assessed similarly by establishing diagnostic plots to explore the distribution and identify the most appropriate regression approach, including stratification factors and baseline covariates within a multilevel model. These plots include residual plots to check for violations like non-linearity and heteroscedasticity, normal probability plots to assess the normality of residuals, and histograms of residuals to identify potential outliers.

Outcomes at the individual level (CYP and school staff) will be analysed using multilevel modelling, while outcomes at the school level will be done through linear regression. Table 5 sets out the statistical analysis for each outcome by level.

Table 5 Statistical analysis by outcome and level

Outcome	Level	Model	Covariates
Primary outcome Externalising behaviour	CYP	Multilevel model	Pre-treatment scores of outcomes at CYP level

¹⁰ This refers to the binary variable indicating whether the school is above or below the median proportion of FSM6 students

Secondary outcomes Internalising behaviour Non-psychotic psychological distress Well-being Sense of connectedness Exclusions, suspensions and attendance at individual (CYP) level			Demographic factors (sex, FSM status) at CYP level
Secondary outcomes Attitudes related to TIC Well-being	School Staff	Multilevel model	Pre-treatment scores of outcomes at staff level
Secondary outcomes Staff retention Staff sickness Exclusions & suspensions of CYP School attendance of CYP	School	Linear regression (OLS)	Pre-treatment scores of outcomes at the school level

The syntax in Stata© would be as below, using the ‘mixed’ command:

```
Full adjusted model: mixed post-treatment_outcome TISUK baseline_outcome fsm || school_id
```

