2.3.1 Primary outcome analysis

The primary outcome combines the Conduct Problems and Hyperactivity sub-scales of the Strengths and Difficulties Questionnaire (SDQ) to measure externalising behaviours.

We will employ a two-level multilevel model to account for the clustered nature of our data, where students are nested within schools. This modelling approach assumes that the schools included in the study represent a random sample from the broader population of schools. Multilevel models are well-suited for analysing hierarchical data structures and appropriately handling the variability within schools (among students) and between schools in terms of

outcomes. These models can effectively capture and model the complex sources of variation at multiple levels of the hierarchy (Bosker & Snijders, 2011).

The two-level **random-intercept model** is described by:

$$Y_{ij} = \beta_1 + TISUK_j\tau + (Baseline_{ij})\beta_2 + FSM_j\beta_3 + \mu_j + \varepsilon_{ij}$$

- Y_{ij} is the outcome for pupil i in school j ;
- $TISUK_j$ is a binary variable denoting whether a school is assigned to the intervention (1) or the control (0);
- $Baseline_{ij}$ represents pupil-level pre-test covariates and demographic characteristics at baseline for pupil i in school j .
- FSM_j is a binary indicator denoting whether a school is above the median proportion of FSM6 (1) or below (0).
- μ_j are the school level residuals [$\mu_j \sim i. i. d N(0, \sigma_\mu^2)$]
- ε_{ij} are the individual level residuals [$\varepsilon_{ij} \sim i. i. d N(0, \sigma_\varepsilon^2)$]

This is a random intercept model because $\beta_{1j} = \beta_1 + \mu_j$ corresponds to the school-level intercept for school j and $\beta_{1j} \sim i. i. d N(\beta_1, \sigma_\mu^2)$. The total variance is decomposed into two portions: the between-school variance (μ_j) and the within-school variance (ε_{ij}). The target parameter of the intervention is the average effect on pupil outcomes captured by τ .

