2.3.3 Sub-group analysis

A priori in the protocol has been set out for the sub-group analysis. The sub-group analysis is exploratory and will be twofold. First, we will conduct a latent class analysis (LCA) on the intervention group to explore whether there are emerging sub-groups with differential effects. Second, we will conduct a multilevel model by sub-groups, considering that a model with interaction may be more demanding regarding power analysis. However, we will also consider a multilevel model with interaction between treatment and sub-group dummy variables for robustness check.

Latent class analysis

LCA refers to the model whose underlying indicators are all categorical, while for the continuous case, LCA is known as latent profile analysis (LPA) (Sinha, Calfee, & Delucchi, 2021). The LCA model will include the socio-demographic variables (sex, ethnicity, FSM) and primary and secondary outcomes. This will allow us to observe 'latent' groups emerging from the data.

In latent class analysis (LCA), the probability of an individual belonging to a particular latent class is modelled based on observed categorical indicators. The model assumes that the observed variables are conditionally independent given the latent class. This analysis is described by the below equation, assuming a Y_{ij} observed categorical variable for individual i in group j . The probability of observing a specific pattern of responses Y_{ij} given the latent class c is modelled using a multinomial logistic regression, typically represented as:

$$P(Y_{ij} = k | C_{ij} = c) = \frac{\exp(\lambda_{kj})}{\sum_{l=1}^K \exp(\lambda_{lj})}$$

Where:

- $P(Y_{ij} = k | C_{ij} = c)$ is the probability of observing response category k for individual i in group j given latent class c .
- K is the total number of response categories.
- λ_{kj} is the log-odds of individual i in group j selecting response category k when belonging to latent class c .

In the context of this analysis plan:

- The observed categorical variables Y_{ij} will include socio-demographic variables (sex, ethnicity, FSM) and primary and secondary outcomes.
- The latent class variable C_{ij} represents the unobserved class membership.
- will be estimated for each response category and latent class combination.

Multilevel model by sub-groups

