The multilevel analysis by groups will explore the differential effects of the intervention by sex, FSM status and ethnicity, described by a modified level-1 equation as below, with φ as the main parameter of interest:

$$Y_{ij} = \beta_1 + TISUK_j\tau + (Group_{ij})\beta_2 + TISUK_j * Group_{ij})\phi + \mu_j + \varepsilon_{ij}$$

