2.3.9 Compliance

We will conduct a Complier Average Causal Effects (CACE) analysis using an instrumental variable framework to explore the impact of compliance on the primary outcomes at different levels of compliance. The CACE analysis will be implemented using a two-stage least squares (2SLS) approach clustering the standard errors, where the first stage models compliance as a function of the randomised treatment assignment, and the second stage models the outcome as a function of the predicted compliance from the first stage and other covariates.

Compliance will be measured at the school level through a binary variable, compliance (Yes/No). Compliance for those schools in the intervention arm will be assessed based on the level of engagement. Section 5 discusses the engagement tool in more detail. The tool assesses engagement across five key dimensions:

- Individual Training,
- Whole Staff Training,
- Consultancy,
- Reflective Supervision,
- Webinars.

Each dimension is scored based on specific criteria, such as the number of staff trained, attendance at meetings, and utilisation of resources. The tool uses a point-based system, with 100 points possible across all dimensions. The final engagement score is calculated as a percentage, with clear thresholds for interpretation:

- up to 50% indicates poor engagement,
- 51-75% moderate engagement,
- 76-90% good engagement, and

- 90-100% excellent engagement.

The engagement score will be used to measure compliance in the CACE analysis. CACE weighs the intention-to-treat (ITT) treatment effect by the proportion of compliance, allowing for the estimation of unbiased treatment effects while maintaining the original randomisation in the analysis. Therefore, a school in the intervention arm will be considered compliant with the trial if showing an engagement of 76% or higher. As a robustness check in the analysis, we will explore how compliance is associated with the outcomes and if any threshold for minimum compliance emerges by setting compliance at 76%, 80% and 90% of the engagement tool. This finding could serve in the future of a trial to establish a minimum threshold that ensures a successful delivery.

As set out in the TOC, the impact on CYP is mediated through a change in policies and procedures at the school level. Measuring compliance on that aspect remains challenging. However, this mediator will be assessed qualitatively through the IPE data collection activities.

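### The exploratory treatment-by-group interaction in SAP 2.3.3 has a school random intercept but no random slope or clustered standard error, so its standard error is too small if the group gap varies between schools

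*SAP*

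**What the plan says.** SAP 2.1 fixes the design: "The unit of randomisation is the school". ERQ11 (SAP 2.3) is the sub-group question. It opens "What is the mean difference in all primary and secondary CYP outcomes between CYP in intervention settings who received TISUK training" and goes on to sex, ethnicity and FSM eligibility.

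SAP 2.3.3 labels the sub-group work exploratory. Its opening paragraph leads with multilevel models fitted by sub-group, on the ground that an interaction model demands more power, and then adds: "we will also consider a multilevel model with interaction between treatment and sub-group dummy variables for robustness check". Protocol 4.1 takes the same line.

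Later 2.3.3 states: "The multilevel analysis by groups will explore the differential effects of the intervention by sex, FSM status and ethnicity". The only equation given there for the multilevel sub-group work is the interaction model, "described by a modified level-1 equation as below, with φ as the main parameter of interest". Its terms are TISUK, Group, TISUK × Group, a school effect μ and a pupil residual ε.

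That equation modifies the model in SAP 2.3.1, of which the SAP says "This is a random intercept model because" its one school-level term shifts only the intercept. The matching Stata line in SAP 2.3 is "mixed post-treatment_outcome TISUK baseline_outcome fsm || school_id". Nothing follows the school identifier, so there is no random slope and no cluster-robust option. In the main-trial plan, clustered errors are named only for the CACE analysis in 2.3.9 ("two-stage least squares (2SLS) approach clustering the standard errors"), and robust errors only for the school-level regressions in 2.3.2.

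**The concern.** TISUK × Group is a cross-level interaction: treatment is set per school, and group membership varies between pupils in a school. The independent pieces of information about φ are the schools' own group gaps, such as boys minus girls.

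A school's random intercept enters both halves of its gap and drops out. It therefore protects the overall treatment effect against clustering but not φ. If the gap differs between schools for reasons unrelated to TISUK, the model counts that variation as independent pupil error and reports too small a standard error.

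At stake are claims that TISUK works better for one sex, for FSM pupils or for one ethnic group. ERQ1 to ERQ10 name ten pupil outcomes and there are three group variables, so about 30 interactions could be tested. With no true interaction, the expected number of false positives is 30 × 0.05 = 1.5 at the nominal rate and 30 × 0.10 = 3 at a 10% rate. Whether to adjust for multiplicity is a separate matter.

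**Working it through.** **Inputs from the documents.** From SAP Table 4: 40 and 38 schools randomised, baseline ICC 0.015, planning ICC 0.03, two-sided α 0.05, power 0.80, stated average cluster size 166, and 13,393 pupils with the baseline primary outcome (13,393/78 = 171.7 per school).

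**Assumed, because the documents do not give them.** The between-school SD of the group gap, *s*, is taken from 0 to 0.15 pupil SD. Group shares *p* are taken as 50%, 25% and 15%.

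**The plan's own figure.** The SAP 2.2 formula with 100 schools, 160 pupils, ICC 0.03 and normal quantiles gives 2.8016 × √(0.03/25 + 0.97/(25 × 160)) = 2.8016 × √0.0014425 = 0.1064, as stated. The documents give no power or error rate for the sub-group test itself.

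**Understatement for φ.** With total pupil variance 1, the sampling variance of one school's gap is w = (1 − ICC)/(m p(1 − p)). For m = 171.7 and p = 0.5, w = 0.985/42.925 = 0.0229. The true variance of the gap is w + s², but the intercept-only model uses w. The variance of φ is therefore understated by the factor

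F = 1 + s² m p(1 − p)/(1 − ICC),

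and the actual error rate is 2 × [1 − Φ(1.96/√F)].

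At s = 0.10, F = 1 + 0.01 × 42.925/0.985 = 1.436, √F = 1.198, 1.96/1.198 = 1.636, and the rate is 10.2%.

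**Results at 171.7 pupils per school.** The simulation used 2,000 trials per setting, 40 v 38 schools of unequal size, a random-intercept fit and a Wald test of φ.

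| Gap SD | Formula, 50% group | Simulated, 50%, same mix in every school | Simulated, 50%, mix varies by school | Formula, 25% | Formula, 15% |
|---|---|---|---|---|---|
| 0 | 5.0% | 4.2% | 5.6% | 5.0% | 5.0% |
| 0.05 | 6.3% | 6.9% | 6.3% | 6.0% | 5.6% |
| 0.10 | 10.2% | 9.8% | 10.9% | 8.9% | 7.6% |
| 0.15 | 16.4% | 15.8% | 17.8% | 13.7% | 11.0% |

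The Monte Carlo standard error is about 0.5 points near 5%.

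**Smaller clusters at follow-up.** Ten per cent attrition from 166 leaves about 149 pupils (166 × 0.9 = 149.4), and 20% leaves about 133 (166 × 0.8 = 132.8). At s = 0.10 with a 50% group, F is 1.378 and 1.338, and the rates are 9.5% and 9.0%.

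**Gap SD at which the rate reaches 10%.** This needs F = (1.960/1.645)² = 1.42.

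| Pupils per school | 50% group | 25% group | 15% group |
|---|---|---|---|
| 171.7 | 0.098 | 0.113 | 0.138 |
| 133 | 0.11 | 0.13 | 0.16 |

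**With the remedy.** School-clustered standard errors around the same random-intercept fit, referred to a t distribution with 76 degrees of freedom, gave 4.1% to 6.2% in every simulated setting, for both the 50% and the 25% group. The random-slope model was not simulated.

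**The case against.** The case on the other side is strong on scope and size.

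- **Scope.** A reader might infer that sub-group findings in general, or the whole answer to ERQ11, carry an inflated error rate. The documents do not support that. The opening of 2.3.3 leads with separate models by sub-group. Within one group, treatment is constant in each school and the random intercept absorbs that group's school variation, so those standard errors are properly clustered. The primary effect in 2.3.1 is equally untouched. Only φ is affected.
- **Status.** The analysis is labelled exploratory, and the interaction is first introduced as a robustness check. SAP 2.3.1 already commits the report to discussing multiple outcomes and the balance of type I and type II error.
- **Size.** A reader might also infer that the false-positive rate is known to be at least double. It is not. The gap variance appears nowhere in the documents, and an intercept ICC is no evidence about it. A gap SD of 0.10 is a slope variance of 0.01, two thirds of the baseline ICC of 0.015. For two equal groups it implies a correlation of about 0.71 between their school effects, which is possible but not shown. At 0.05 the inflation is slight, and attrition or a smaller group takes the rate at 0.10 below 10%.

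All of this stands, and it limits the point without removing it. Separate models do not test whether two groups differ, so a formal claim of a differential effect would rest on φ. The later text of 2.3.3 also makes φ the main parameter, which conflicts with its role as a robustness check.

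**Conclusion.** The concern holds for φ alone. As specified, its standard error is too small whenever the group gap varies between schools, and nothing else in the plan corrects this.

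The size is conditional on the assumed gap SD, group share and cluster size. Doubling of the nominal 5% needs a gap SD of roughly 0.10 to 0.16 pupil SD over the group shares and cluster sizes examined. These figures use an outcome not adjusted for baseline, in line with the printed sub-group equation, which has no baseline term. Severity is minor: the analysis is exploratory, and neither the primary result nor the by-group models change. The two statements in 2.3.3 about the role of the interaction need to be reconciled.

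**What to change.** In SAP 2.3.3, for every ERQ11 pupil-level interaction:

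1. Add a school-level random slope for the group variable and report φ with school-clustered standard errors, for example `mixed y i.TISUK##i.group ... || school_id: group, covariance(unstructured) vce(cluster school_id)`, with `group` coded 0/1.
2. State the fallback in advance: if the slope variance is estimated at zero or the model does not converge, keep the random intercept and report φ with school-clustered standard errors.
3. Say whether the by-group models or φ lead, so that the opening paragraph and the equation agree.

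This takes a line or two of wording and syntax and no new data. The cost is somewhat wider intervals for φ. For a 50% group at 171.7 pupils per school, the detectable interaction without gap variation is 2.8016 × √[0.0229 × (1/40 + 1/38)], about 0.096 SD. With a gap SD of 0.10 it is 2.8016 × √[0.0329 × (1/40 + 1/38)], about 0.115 SD. That loss of precision is already present if the gap varies; the present model does not show it.

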2.3.4 Further analysis

Additional analysis will be conducted at baseline after randomisation to check the balance between arms and at the follow-up stage. Incorporating the proportion of pupils with FSM status in the randomisation mechanism is designed to improve the balance across arms. After baseline testing, the evaluation team will check balances across arms. If, by chance, randomisation had not achieved the desired balance on those key socio-demographic characteristics that may affect outcomes, we may consider a multilevel analysis of covariance (ML-ANCOVA) as an additional model to test the robustness of our results. Nevertheless, if the randomisation incorporates % of FSM, it is unlikely that there is an imbalance across arms on FSM.

Stepwise regression analysis will be performed to model the relationship between pre-randomisation factors and demographics on observed outcomes at 15 months. Interaction terms with the allocation arm will be included in the analysis, and a significance level of 0.1 will be used to determine which factors are to be included in the regression model. Pre-randomisation factors will include pupil sex, FSM status and ethnicity. This analysis will be augmented by an additional analysis including participants in the intervention arm using the same pre-randomisation factors, process measures of intervention delivery, and staff changes in perceptions of trauma-informed care (this is for the regression analysis at school staff level).

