Stepwise regression analysis will be performed to model the relationship between pre-randomisation factors and demographics on observed outcomes at 15 months. Interaction terms with the allocation arm will be included in the analysis, and a significance level of 0.1 will be used to determine which factors are to be included in the regression model. Pre-

randomisation factors will include pupil sex, FSM status and ethnicity. This analysis will be augmented by an additional analysis including participants in the intervention arm using the same pre-randomisation factors, process measures of intervention delivery, and staff changes in perceptions of trauma-informed care.

Table 6 sets out the statistical analysis for each outcome by level.

Table 6 Statistical analysis by outcome and level

Outcome	Level	Model	Covariates
Primary outcome Externalising behaviour Secondary outcomes Internalising behaviour Non-psychotic psychological distress Well-being Sense of connectedness Exclusions, suspensions and attendance at individual (CYP) level	CYP	Multi-level model	Pre-treatment scores of outcomes at CYP level Demographic factors (sex, FSM status) at CYP level
Secondary outcomes Attitudes related to TIC Well-being	School staff	Multi-level model	Pre-treatment scores of outcomes at staff level
Secondary outcomes Staff retention Staff sickness Exclusions & suspensions of CYP School attendance of CYP	School	Linear regression (OLS)	Pre-treatment scores of outcomes at school level

Sub-group analysis

The sub-group analysis will be twofold. First, we will conduct a latent class analysis (LCA) on the intervention group to explore whether there are emerging sub-groups with differential effects. LCA refers to the model whose underlying indicators are all categorical while for the continuous case, LCA is known as latent profile analysis (LPA) (Sinha, Calfee, & Delucchi, 2021). The LCA model will include the socio-demographic variables (sex, ethnicity, FSM) together with primary and secondary outcomes. This will allow us to observe 'latent' groups emerging from the data.

Second, we will conduct multilevel model by sub-groups considering a model with interaction may be more demanding in terms of power analysis. However, we will also consider for robustness check a multilevel model with interaction between treatment and sub-group dummy variable.

Missing data

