Regarding the risk of having several outcomes, we have designated a primary outcome and several secondary outcomes in this trial, with the primary hypothesis being addressed through the primary outcome measure. While adjustment for multiple testing is a commonly advocated strategy to mitigate the risk of type I error—incorrectly concluding an effect due to a sampling artefact—this approach has the trade-off of potentially increasing the likelihood of type II errors, where a true effect is overlooked. Given the structure of this trial, where a clear distinction is made between the primary and secondary outcomes, strict adjustment for multiple testing may not be necessary. However, it is crucial to discuss the implications of our findings in a nuanced manner in the final report, considering the context of multiple outcomes and the balance between type I and type II error risks. This approach aligns with the understanding that while avoiding false positives is important, it should not come at the cost of missing genuine effects, as discussed in Zhang, Quan, Ng, and Stepanavage (1997).

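### The stepwise moderator analysis at p<0.1 duplicates an unselected interaction model, and the terms it keeps would have exaggerated estimates and intervals that are too narrow

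*SAP*

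**What the plan says.** SAP 2.3.4 (Further analysis) and Protocol 4.1 (Analysis) carry the same plan. The method is stated as follows: "Stepwise regression analysis will be performed to model the relationship between pre-randomisation factors and demographics on observed outcomes at 15 months". On moderation by arm, the SAP adds: "Interaction terms with the allocation arm will be included in the analysis". The inclusion rule comes in the second half of that sentence, where it is said that "a significance level of 0.1 will be used to determine which factors are to be included in the regression model". The candidates are named: "Pre-randomisation factors will include pupil sex, FSM status and ethnicity". A second analysis, restricted to the intervention arm, adds "process measures of intervention delivery, and staff changes in perceptions of trauma-informed care". Having one arm only, it cannot contain an allocation interaction.

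Three other parts of the SAP bear on this:

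- Section 2.3.3 already covers the same moderators without selection: "The multilevel analysis by groups will explore the differential effects of the intervention by sex, FSM status and ethnicity". It gives an equation with a treatment-by-group term as the target. It also says: "The sub-group analysis is exploratory and will be twofold".
- Section 2.3.1 takes the position that "strict adjustment for multiple testing may not be necessary", and leaves multiplicity to discussion in the final report.
- Section 2.3 states that individual-level outcomes are analysed with multilevel models.

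Section 2.3.4 does not repeat the exploratory label or say how its results rank against those of 2.3.3. It does not give the direction of stepping or say whether main effects stay with their interactions. It also does not say whether the 0.1 level applies to main effects, interactions or both.

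**The concern.** Data-driven selection is useful when there are too many candidates to fit together. Here three are named, and all three interactions fit easily in one model. What selection adds is a final model that depends on the data, whose ordinary p-values and intervals ignore how the terms were chosen.

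The plan would also give two answers to one question. Sections 2.3.3 and 2.3.4 address the same three moderators by different methods, and no text says which prevails if they disagree. Analysis by sex, ethnicity and FSM is the subject of ERQ11 and a stated equity commitment (Protocol section 7). An interaction kept at a lenient threshold could therefore be read as evidence about who benefits.

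**Working it through.** The documents give no false-positive rate or power for this analysis, so there is no planned figure to reproduce. The only stated number is the 0.1 level, taken here as two-sided.

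**Inputs.** Three candidate factors and the 0.1 level (SAP 2.3.4). Ten pupil outcomes, ERQ1 to ERQ10 (SAP 2.3). For the simulation: 78 schools (40 and 38), 13,393 pupils at baseline and ICC 0.015 (SAP Table 4). That is 13,393/78 = 171.7, so 172 pupils per school.

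**1. Is selection needed?** A fixed model has an intercept, arm, baseline score, stratum, three factors and three interactions: 10 coefficients if ethnicity is binary. At 60% pupil retention, the lowest rate in SAP Table 2, 13,393 × 0.6 = about 8,036 pupils remain, or roughly 800 per coefficient. Selection saves nothing.

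**2. What selection does to a null term that is kept.** Keeping a term at p<0.1 means |z| > 1.645.

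- Mean |z| without selection: √(2/π) = 0.80.
- Mean |z| once kept: φ(1.645)/0.05 = 0.1031/0.05 = 2.06.
- Share of kept null terms whose 95% interval excludes zero: 0.05/0.10 = 50%. Coverage after selection is therefore 50%, not 95%.

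**3. Chance of keeping a false interaction, if interactions are screened.** With three independent null tests:

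- at 0.10: 1 − 0.9³ = 27.1% per outcome;
- at 0.05: 1 − 0.95³ = 14.3%;
- at 0.05/3: 1 − (1 − 0.0167)³ = 4.9%.

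The simulation (2,000 runs) used a random-intercept model with no true interactions and backward removal of interactions at p≥0.1. It assumed independent binary factors with prevalences of 50%, 25% and 30%.

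| Quantity, per outcome | Simulated |
|---|---|
| At least one interaction kept by the stepwise rule | 28.1% |
| Mean number of false interactions kept | 0.31 |
| At least one p<0.05 after stepwise selection | 14.7% |
| At least one p<0.05 in the full model, no selection | 14.7% |
| At least one p<0.05/3 in the full model | 4.6% |
| Joint 3-df test p<0.05 in the full model | 4.7% |

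The two 14.7% rows are informative. With three roughly independent factors, stepping itself does not raise the rate of p<0.05 findings. The 27% comes mainly from the 0.1 threshold and the lack of multiplicity control.

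**4. Across outcomes.** If the rule is run on all ten pupil outcomes, 30 × 0.10 = 3.0 false interactions are expected. This count does not require the outcomes to be independent. The chance of at least one lies between 27% (outcomes perfectly correlated) and 1 − 0.9³⁰ = 96% (independent).

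**5. Sensitivity.** If the factor effects vary between schools (assumed SD 0.1) and no random slope is fitted, the simulated 28.1% rises to 40.2% (1,000 runs). The joint test then rejects in 12.4% of runs.

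**The case against.** The strongest reply is that an unselected analysis of these moderators is already planned. Section 2.3.3 has subgroup models and an interaction model for sex, FSM status and ethnicity, and calls them exploratory. Section 2.3.4 is headed as further analysis, and nothing says it replaces 2.3.3. That stands, and it rules out the inference that every claim about who benefits would rest on selected interactions.

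Four other stronger readings are tempting but not supported:

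- **That 27% is the error rate of the stated rule.** The text applies 0.1 to factors and says separately that interactions are included. A fair reading is that factors are screened and interactions are fitted regardless. The 27% is conditional on interactions being screened.
- **That stepwise selection itself produces the false positives.** The simulation shows otherwise. Selection adds selective emphasis and invalid intervals for the terms it keeps.
- **That clustering would be ignored.** Section 2.3.4 does not mention the school random effect, but section 2.3 states multilevel modelling for individual-level outcomes and 2.3.4 does not override it.
- **That only the selected model would be reported.** This is a natural inference, but no reporting rule is given.

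It is also fair that section 2.3.1 promises to interpret results in the light of multiple outcomes. That helps the discussion but does not correct an interval computed after selection.

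**Conclusion.** The stepwise step should go, for three reasons. It is unnecessary with three named factors, it gives invalid estimates and intervals for the terms it keeps, and it is neither labelled exploratory nor ranked below section 2.3.3.

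The size is about 27% per outcome for at least one false interaction, and about three false interactions over ten outcomes. Both figures assume that the 0.1 rule screens interactions and that ethnicity is binary. The 27% also assumes roughly independent factors, and the count of three assumes the rule is run on every pupil outcome. The main-trial plan gives no ethnicity grouping (only the embedded quasi-experimental study collapses it to two groups, SAP 3.4.5), and more levels would add tests.

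The harm is confined to secondary moderator findings. A reader might infer that the trial's main result is at risk. It is not, because the primary model in SAP 2.3.1 involves no selection and its intention-to-treat estimate is unaffected.

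**What to change.** In SAP 2.3.4, delete the stepwise step for the allocation-interaction analysis. In its place:

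- Fit one multilevel model per pupil outcome with arm, baseline outcome, FSM6 stratum, sex, FSM status, ethnicity and all three arm interactions. The equation in 2.3.3 shows neither the baseline outcome nor the stratum.
- State the ethnicity coding in advance.
- Report every interaction with its confidence interval, whatever its p-value.
- Use one joint test of the interactions per outcome, or a Holm adjustment. Dropping selection alone is not enough, since three tests at 0.05 still leave about 14% per outcome. The joint test brings this to about 5%, or 10 × 0.05 = 0.5 outcomes expected to be flagged falsely. This holds if the factor effects do not vary materially between schools. If they may, random slopes for the factors should be considered.
- Label the analysis exploratory, as in 2.3.3, and say that it is the single source for treatment-by-factor results.

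The cost is SAP wording and less analysis than now planned. The one downside is a slightly smaller chance of flagging any single interaction. The intervention-arm analysis of process and staff measures is a separate matter and need not change for this point.
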